### **3.2 Inclusion/Exclusion Criteria**

Inclusion criteria are as follows: 1) willingness to participate in the study; 2) less than 20 weeks' gestation 3) able to speak Dangme, Ga, Akan, Ewe, or English; 4) over the age of 15 years; and 5) no history of medical problems that would indicate the participant might be considered "high risk" (e.g., hypertension, insulin-dependent diabetes mellitus) and thus requiring a more individualized approach to care.

In the eastern region, 10.4% of females age 15-49 have never attended school and only 15.7% percent have completed secondary school or higher. Thus, we will not limit participation based on literacy, however we will control for years of education and literacy status in the analysis. This is a study of an intervention for pregnant women to improve maternal and newborn outcomes; thus no males will be included.

### 3.3 Data Collection and Measures

All quantitative data will be collected by trained RAs using encrypted and password protected tablets and the REDCap secure web application for data collection database management. Redcap, a secure web application, is geared to support online or offline data capture for research studies. When internet connection is not available, data will be collected off-line and stored on the encrypted tablet. Once a connection is available, these data will be uploaded, managed, and stored on a secure server.

No data will be collected by clinical providers. Data collection will occur at five time points in both intervention and control arms:

1. Time 0: at ENROLLMENT (in person)
  2. Time 1: at THIRD TRIMESTER (in person)
  3. Time 2: POST BIRTH up to 6 weeks after delivery (in person)
  4. Time 3: SIX MONTHS POSTPARTUM (by phone)
  5. Time 4: ONE YEAR POSTPARTUM (by phone)
- 
- 1) T0: The baseline session occurs immediately following the consent process and will be held for approximately 1 hour. Data will be collected by trained RAs using a structured survey; medial information will be self-reported, and thus, are not protected health information (PHI).
  - 2) T1: This session will occur at the third trimester of pregnancy and will last 45 – 60 minutes. Data will be collected by trained RAs using a structured interview and retrieving data from the ANC card. Data collected from the ANC card are PHI and will be protected.
  - 3) T2: This session will occur in the period immediately to 6 week after delivery and will last 45 – 60 minutes. Data will be collected by trained RAs using a structured interview and information from ANC cards on maternal and newborn clinical outcomes using a pre-determined set of indicators.
  - 4) T3: This session will occur 6-months postpartum; data will be collected via phone by a trained RAs using a structured interview. This session will take approximately 20 - 30 minutes.
  - 5) T4: This session will occur 1-year postpartum; data will be collected via phone by a trained RAs using a structured interview. This session will take approximately 20 - 30minutes.

During all visits midwives will record Clinical Health Related Outcomes (Place of birth, hemoglobin levels, newborn birth weight, maternal & newborn morbidities, stillbirth, postpartum visit within 2 days post birth) on the women's ANC card. These data will be collected by the RA during all study visits except baseline.

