### **1.1 Ghanaian Context**

In 2015, the maternal mortality ratio in Ghana was estimated at 319 per 100,000 live births – placing a woman’s lifetime risk of maternal death at 1 in 74, compared to 1 in 3,800 in the United States. In 2014, while 87.3% of women in Ghana surveyed had attended the minimum standard of 4 antenatal care (ANC) visits, 27% gave birth alone or with a non-skilled attendant. Sixty-eight percent of all deaths among children under age 5 in Ghana happen before a child’s first birthday, with 48% of deaths occurring in the first month of life - making the first 28 days in an infant’s life crucial for survival. Only 22.8% of newborns received the recommended postnatal check-up within the first two days of life between 2012-2014 in Ghana. It should be noted that since 2008 there has been only a marginal decline (3%) in neonatal mortality within Ghana. Ghana is now one of 24 priority countries targeted by the United States Agency for International Development (USAID) to improve maternal and child health and end preventable deaths.

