### Primary Outcomes

- Attendance at 4+ ANC visits
- Facility birth
- Four postnatal/postpartum check-ups for both mother and newborn in the first 6 weeks after birth

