## Measures

Time Point	Domain	Data collection
T0 – Baseline	Demographic Characteristics (Age, gravida, living children, marital status, age at marriage, pregnancy history, medical history)	Face-to-face Survey
	Self-efficacy	
	Recognize problems and understands health information	Face-to-face Survey
	Care-seeking history	Face-to-face Survey
	Educational Background	
	Level of Education	Face-to-face Survey
	Prior Knowledge	
	Ability to identify danger signs/BPCR	Face-to-face Survey
	Health Literacy Skills (understanding, engagement with health system)	Face-to-face Survey
	Ecological Influences (social support, community and family resources)	Face-to-face Survey
T1 – Third trimester	Comprehension of Stimuli (identification of danger signs, BPCR)	Face-to-face Survey
	Self-determination	
	Intent to use family planning / preparation for birth	Face-to-face Survey
	Two or more tetanus toxoid vaccines / Completion of ITP 2 malaria prophylaxis	ANC Card
T2 – Post birth	Clinical Health Related Outcomes (Place of birth, hemoglobin levels, newborn birth weight, maternal & newborn morbidities, stillbirth, postpartum visit within 2 days post birth)	ANC Card
	Self-determination	
	Attendance at 4 or more ANC visits	ANC Card
	Adherence to care - Number of ANC Visits	ANC Card
	Health Related Behavior (Maternal and newborn postpartum visits)	Survey
	Clinical Health Related Outcomes (Perinatal mortality (<7 days), maternal morbidities)	ANC Card
T3 – Six months postpartum	Health Related Behavior (Uptake of modern family planning, exclusive breastfeeding, 4 postnatal check-ups completed on both mother and newborn in first 6 weeks)	Survey via phone
	Clinical Health Related Outcomes (Neonatal mortality(<28 days), maternal morbidities)	Survey via phone
T4 – One year postpartum	Health Related Behavior (Repeat pregnancy)	Survey via phone
	Clinical Health Related Outcomes (Infant immunized per EPI schedule; maternal morbidities)	Self-report Survey via phone

During all visits midwives will record Clinical Health Related Outcomes (Place of birth, hemoglobin levels, newborn birth weight, maternal & newborn morbidities, stillbirth, postpartum visit within 2 days post birth) on the women's ANC card. These data will be collected by the RA during all study visits except baseline.

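### Facility birth, an Aim 2 primary outcome, has the midwife-completed ANC card as its only named source, with no stated T2 question on place of birth and no rule for a blank entry

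*Combined protocol and SAP*

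**What the plan says.** Section 2.0 lists "Facility birth" among the Aim 2 primary outcomes. Section 4.0 analyses it with a logit-link mixed model, tests it at 0.05 and reports an odds ratio.

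Section 3.3 describes the recording route: "During all visits midwives will record Clinical Health Related Outcomes (Place of birth, hemoglobin levels, newborn birth weight" and further items, on the woman's ANC card. The research assistant (RA) then takes the entries from the card: "These data will be collected by the RA during all study visits except baseline".

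In the Measures table, the T2 row that holds "Place of birth, hemoglobin levels, newborn birth weight, maternal & newborn morbidities, stillbirth, postpartum visit within 2 days post birth" gives the ANC card as its source. A separate T2 row, for maternal and newborn postpartum visits, gives a survey. The table thus separates card items from interview items and puts place of birth with the card. No later row lists it.

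T2 is held in person in both arms, at any time from birth to 6 weeks. The text on that session says: "Data will be collected by trained RAs using a structured interview and information from ANC cards on maternal and newborn clinical outcomes". It does not list the interview questions. Section 4.0 states intention to treat, but gives no method for missing outcomes and no sensitivity analysis.

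**The concern.** The recording route is tied to the outcome. A woman who delivers in a facility is among staff who can complete the card. A woman who delivers elsewhere gets an entry only if she later attends a midwife, and only if that happens before the RA reads the card. T2 is the only in-person study contact after birth, and it can fall early in its 6-week window.

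The protocol's background suggests that later contact cannot be taken for granted: "27% gave birth alone or with a non-skilled attendant", and "Only 22.8% of newborns received the recommended postnatal check-up within the first two days of life". Blanks are therefore plausibly more frequent when the true value is a non-facility birth.

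Their frequency may also differ by arm. The trial hypothesises more facility births and more postnatal attendance in the group arm. If attendance rises, more of that arm's non-facility births reach the card, so the completeness of one Aim 2 primary outcome would depend on success on another. With no rule for blanks, the default model fit drops those women.

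**Working it through.** The plan gives no expected facility-birth rate, effect size or allowance for missing data, so there is no figure of its own to reproduce here. What follows is an illustration.

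**Inputs**
- True control rate p = 0.73. Assumption: 1 − 0.27, using the figure in section 1.1 on birth without a skilled attendant as a stand-in for non-facility birth.
- True group-arm rate p = 0.80. Assumption.
- m = share of non-facility births with no place of birth on the card. Assumption, varied by arm.
- Every facility birth is recorded. Assumption, relaxed below.
- Women with a blank entry are dropped. Assumption, since no rule is stated.

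**Formulas**
- Observed rate = p / [p + (1 − p)(1 − m)]
- Share of all women missing = (1 − p)m
- Observed odds ratio = true odds ratio × (1 − m in control) / (1 − m in group)

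True odds ratio: (0.80/0.20) / (0.73/0.27) = 4.000 / 2.704 = 1.48.

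**Results**

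| True rates, control / group | m, control / group | Observed rates, control / group | Difference (points) | Odds ratio |
|---|---|---|---|---|
| 73% / 80% | 0 / 0 | 73.0% / 80.0% | 7.0 | 1.48 |
| 73% / 80% | 0.25 / 0.25 | 78.3% / 84.2% | 5.9 | 1.48 |
| 73% / 80% | 0.50 / 0.50 | 84.4% / 88.9% | 4.5 | 1.48 |
| 73% / 80% | 0.50 / 0.30 | 84.4% / 85.1% | 0.7 | 1.06 |
| 73% / 80% | 0.30 / 0.50 | 79.4% / 88.9% | 9.5 | 2.07 |
| 73% / 73% | 0.50 / 0.30 | 84.4% / 79.4% | −5.0 | 0.71 |
| 73% / 73% | 0.30 / 0.50 | 79.4% / 84.4% | 5.0 | 1.40 |

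Worked example, fourth row. Control: 0.73 / (0.73 + 0.27 × 0.50) = 0.73 / 0.865 = 84.4%. Group: 0.80 / (0.80 + 0.20 × 0.70) = 0.80 / 0.94 = 85.1%. Odds ratio: 1.48 × 0.50 / 0.70 = 1.06.

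In the third row, 0.27 × 0.50 = 13.5% of control women and 0.20 × 0.50 = 10.0% of group-arm women are missing.

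**Relaxing full recording of facility births.** If a share f of facility births is also blank, the observed odds are p(1 − f) / [(1 − p)(1 − m)]. The rate is inflated only if m exceeds f. The odds ratio is biased only if (1 − f)/(1 − m) differs between arms.

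These are marginal odds ratios, without covariates or the facility random effect.

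**The case against.** The strongest reply is that the plan already has two safeguards. Midwives make entries at all visits, not only at delivery, so a birth elsewhere can be entered at a later postnatal visit. The RA also meets women in person at T2 in both arms, and the sentence on that session can be read as letting the interview and the card both serve the clinical outcomes. The instrument is not in the documents, so nobody can say that the question is left out.

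This stands against a stronger reading that a reader might reach: that a woman who gives birth outside a facility has no one to record it, so that the outcome goes missing mainly when its value is no. The documents do not support that. A later entry is possible, and the preponderance of non-facility births among blanks is inferred from the recording route, not documented. Facility births could leave blanks too, for instance when a woman delivers somewhere other than her ANC site.

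The background figures are also weak guides to size. The 27% is national, from 2014, and measures attendance rather than place. It is not an upper bound on non-facility birth in women already registered for ANC. The 22.8% covers newborn checks within two days, whereas a card entry could be made at any visit before T2.

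The objection does not supply a source or a rule. The table names only the card, no text says that the interview asks place of birth, and nothing says which source prevails or what a blank means.

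**Conclusion.** The point holds as a weakness in how a primary outcome is sourced. Followed as written, the plan exposes facility birth to missingness that is plausibly related to its own value, when a better source is available at a contact already scheduled. It should be changed.

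Its size cannot be fixed from the documents. With equal loss in both arms, the odds ratio, which is the planned effect measure, is unaffected. The rates are inflated and the difference shrinks, from 7.0 to 4.5 points at 50% loss. With unequal loss the odds ratio is biased, and the direction depends on which arm loses more: a true 1.48 becomes 1.06 or 2.07, and a true null becomes 0.71 or 1.40, at losses of 50% and 30%.

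A reader might infer that the bias must hide a benefit or create apparent harm. The hypothesis of better postnatal attendance makes that direction plausible, but the documents do not establish it. All loss rates, the 73% and 80%, the full recording of facility births and the dropping of blanks are assumptions.

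**What to change.** In the T2 rows of the Measures table, add the face-to-face interview as a source for place of birth, asked of every woman in both arms, including after a stillbirth or neonatal death. Cross-check the answer against the ANC card, state in advance which source prevails when they disagree, and report disagreement by arm.

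If T2 is missed, use the card where it can be obtained, or ask at the T3 call. Treat women with no source as missing and report their number by arm.

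In section 4.0, add a sensitivity analysis that counts these women as non-facility births. Under the full-recording assumption above, this restores the true rates exactly (73% and 80%). If some facility births are also without a source, it understates facility birth.

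The cost is one question in an existing interview, a fallback question at T3, and a few lines in the table and section 4.0. The downside is self-report by unblinded women, who may over-report facility birth, possibly more so in the arm that promotes it; reporting disagreement with the card by arm makes that visible. Women asked only at T3 would be recalling over about 6 months, although place of birth is a simple fact to recall.

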## Measures

Time Point	Domain	Data collection
T0 – Baseline	Demographic Characteristics (Age, gravida, living children, marital status, age at marriage, pregnancy history, medical history)	Face-to-face Survey
	Self-efficacy	
	Recognize problems and understands health information	Face-to-face Survey
	Care-seeking history	Face-to-face Survey
	Educational Background	
	Level of Education	Face-to-face Survey
	Prior Knowledge	
	Ability to identify danger signs/BPCR	Face-to-face Survey
	Health Literacy Skills (understanding, engagement with health system)	Face-to-face Survey
	Ecological Influences (social support, community and family resources)	Face-to-face Survey
T1 – Third trimester	Comprehension of Stimuli (identification of danger signs, BPCR)	Face-to-face Survey
	Self-determination	
	Intent to use family planning / preparation for birth	Face-to-face Survey
	Two or more tetanus toxoid vaccines / Completion of ITP 2 malaria prophylaxis	ANC Card
T2 – Post birth	Clinical Health Related Outcomes (Place of birth, hemoglobin levels, newborn birth weight, maternal & newborn morbidities, stillbirth, postpartum visit within 2 days post birth)	ANC Card
	Self-determination	
	Attendance at 4 or more ANC visits	ANC Card
	Adherence to care - Number of ANC Visits	ANC Card
	Health Related Behavior (Maternal and newborn postpartum visits)	Survey
	Clinical Health Related Outcomes (Perinatal mortality (<7 days), maternal morbidities)	ANC Card
T3 – Six months postpartum	Health Related Behavior (Uptake of modern family planning, exclusive breastfeeding, 4 postnatal check-ups completed on both mother and newborn in first 6 weeks)	Survey via phone
	Clinical Health Related Outcomes (Neonatal mortality(<28 days), maternal morbidities)	Survey via phone
T4 – One year postpartum	Health Related Behavior (Repeat pregnancy)	Survey via phone
	Clinical Health Related Outcomes (Infant immunized per EPI schedule; maternal morbidities)	Self-report Survey via phone

During all visits midwives will record Clinical Health Related Outcomes (Place of birth, hemoglobin levels, newborn birth weight, maternal & newborn morbidities, stillbirth, postpartum visit within 2 days post birth) on the women's ANC card. These data will be collected by the RA during all study visits except baseline.

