### 4.0 Data Analysis (Aims 1-3)

Data on all patients randomly assigned to the intervention or control groups will be analyzed on an intention-to-treat basis. Deviations from randomized allocation will be reported. Summary statistics based on mean, standard deviation or frequency will be used to characterize the sample distribution of each arm. Proper transformations will be investigated and taken if the sample distributions of continuous variables violate the normality assumption. For Aims 1-3, generalized linear mixed models (GLMMs) will be used to test the differences between the two arms since cluster randomized control design is used. There are four components in GLMMs: outcome variable, fixed effects, random effect, and link function. The fixed effects include explanatory variable and covariates. In this study, all three aims have the same explanatory variable which is a binary variable indicating the arm to which women are assigned. The study sites, gestational age, and women's demographic variables such as education or literacy, marital status, pregnancy history, and medical history will be added to the GLMMs as covariates to increase the precision of estimates. The random effect is the 14 facilities. In this study, a random intercept model will be used to account for the cluster effect. The outcome variables and link functions in GLMMs depends on aims and are described below. The construct of GLMMs is to test if the explanatory variable is significant at 0.05 level using likelihood ratio test.

For **Aim 1** to quantify differences in the recognition of pregnancy and newborn danger signs and knowledge of recommended action steps, the BPCR Index will be measured at enrollment and third trimester. We will add baseline data as covariates. The logit link function will be used for each binary BPCR question to test the efficacy of the group-based ANC method. The identity link function will be used when the outcome variable is a summary statistic of the BPCR Index. When the p-value of the explanatory variable is less than 0.05, we will declare a significant difference between the two arms. Average changes in BPCR summary statistics or odds ratio in each question will be used to quantify the effect of the group-based ANC intervention.

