For **Aim 2** of assessing behavioral differences in care-seeking patterns between the two arms, the outcome variables are number of attendances in ANC visits, facility birth, and postnatal/partum care. For the attendance outcome variable, identity function will be used. For facility birth or postnatal/partum care, the logit link function is used. When the p-value of the explanatory variable is less than 0.05, we will declare a significant difference between the two arms. The effect of group-based ANC on attendances is quantified by the average difference. The effects of group-based ANC on facility birth and postnatal/partum care are quantified by odds ratio. For the secondary outcomes in aim 2, the logit or identity links will be used in the way similar to the primary outcomes.

For **Aim 3** to evaluate the clinical outcomes of mothers and their newborns, the outcome variables are maternal pregnancy-related morbidities and newborn birth status. For maternal morbidities, the logit link function is used. Since the newborn birth status is classified into three categories (stillbirth, live birth, and early neonatal mortality), cumulative logit link function is used. When the explanatory variable is significant at 0.05, the effect of group-based ANC on maternal pregnancy-related morbidities and newborn birth status are interpreted using odds ratio. We will illustrate the difference between outcomes using odds ratios for each pair of newborn birth status. The secondary outcomes are analyzed similarly using identity or logit link functions.

For the multiple outcomes in the same family, we will conduct direct inference using the Holm's multiple testing procedure to control familywise error rate at 0.05 level. The GLMM analysis will be carried out using lme4 package from R software. All findings will be reported using the Consolidated Standards of Reporting Trials (CONSORT) statement as a guide. Full transparency will be provided when reporting experimental details so that others may reproduce and extend our findings. We will register the study with clinicaltrials.gov and disclose all demographic and baseline characteristics, as well as primary and secondary outcomes.

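### The Aim 2 primary outcome of four postnatal check-ups is listed as a count only in the six-month phone survey, and no rule says how to score it after a stillbirth or early infant death

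*Combined protocol and SAP*

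**What the plan says.** Section 2.0 lists as an Aim 2 primary outcome "Four postnatal/postpartum check-ups for both mother and newborn in the first 6 weeks after birth". Section 4.0 treats it as binary: "For facility birth or postnatal/partum care, the logit link function is used".

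The Measures table in section 3.3 puts the four-visit item, "4 postnatal check-ups completed on both mother and newborn in first 6 weeks", at T3, with a phone survey as the source. Section 3.3 describes T3 in the same way: "This session will occur 6-months postpartum; data will be collected via phone by a trained RAs using a structured interview".

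Two earlier items touch on the same visits. At T2 the table has a survey item, "Maternal and newborn postpartum visits", with no number attached. Among the data taken from the ANC card, the only postnatal visit named is the "postpartum visit within 2 days post birth". On the timing of T2, section 3.3 says "This session will occur in the period immediately to 6 week after delivery and will last 45 – 60 minutes".

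On the analysis set, section 4.0 says "Data on all patients randomly assigned to the intervention or control groups will be analyzed on an intention-to-treat basis". Neither 2.0 nor 4.0 says how this outcome is scored when there is no living newborn, and no section says which of T2, T3 or the card is the source of record.

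**The concern.** There are two separate weaknesses in one primary outcome.

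**Source.** The woman must recall two counts, her own check-ups and her baby's, and place them inside a window that closed months earlier. A cut-off at four makes the result depend on women at three or four visits, where an error of one visit flips the category. Error of equal size in both arms shrinks a real effect. Error that differs by arm can create a false one. The other Aim 2 attendance outcome, four or more ANC visits, is taken from the ANC card, so the postnatal primary has the weaker source and the plan gives no reason.

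**Rule.** After a stillbirth the newborn half of the criterion cannot be met, and the same holds if the infant dies before a fourth check-up. Scoring such a woman as a failure mislabels a mother who attended all her own check-ups. Excluding her makes the analysed set depend on birth outcome, which is an Aim 3 primary outcome that the intervention is meant to improve. With no rule written down, the choice stays open until the data are in.

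**Working it through.** The plan states no rate, power figure or sample-size calculation for this outcome, so there is no figure to reproduce. All rates below are assumptions except where a section is named.

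**1. Recall gap.** T3 is at six months, about 26 weeks. The window closes at 6 weeks. 26 − 6 = 20 weeks.

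**2. Does an earlier item cover the count?**

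| Item | Where listed | Covers four visits for both, to week 6? |
|---|---|---|
| Postpartum visits, survey | T2, in person | Not assured: no count named, and T2 can precede week 6 |
| Visit within two days | Card | No: one visit only |
| Four check-ups for both | T3, phone | Yes, by recall |

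**3. Effect of recall error.** With true rate p, sensitivity Se and specificity Sp, the observed rate is Se·p + (1 − Sp)(1 − p).

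Equal error in both arms, true rates 50% and 60% (10 points, OR 1.50):

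| Se = Sp | Observed rates | Difference | OR |
|---|---|---|---|
| 0.95 | 50% and 59% | 9 points | 1.44 |
| 0.90 | 50% and 58% | 8 points | 1.38 |
| 0.80 | 50% and 56% | 6 points | 1.27 |

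Unequal error with no true effect, p = 50% and Se = 0.90 in both arms. The false difference is the gap in specificity times (1 − p):
- Sp 0.85 against 0.90: 0.05 × 0.50 = 2.5 points.
- Sp 0.80 against 0.90: 0.10 × 0.50 = 5 points.

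**4. Effect of coding losses as failures.** Let m be the share of women with a stillbirth, or an infant death before the fourth check-up. Let r be the relative reduction in m under the intervention. The control arm shows p(1 − m) and the intervention arm p(1 − m(1 − r)), so with no true effect on care-seeking the spurious difference is p·m·r.

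Inputs: m = 2–5% and p = 50% (assumptions). r = 9–23%, the reductions in stillbirths and neonatal mortality that section 1.2 cites for community women's groups, used for illustration only.
- Low end: 0.50 × 0.02 × 0.09 = 0.0009, or 0.09 points.
- High end: 0.50 × 0.05 × 0.23 = 0.00575, or 0.58 points.

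Over p = 20–80% the range widens to 0.20 × 0.02 × 0.09 = 0.04 points and 0.80 × 0.05 × 0.23 = 0.92 points.

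If losses are equal by arm, a true 10-point difference becomes 10(1 − m), that is 9.8 to 9.5 points. With 1680 women split equally (840 per arm, an assumption), m = 2–5% is about 17 to 42 women per arm.

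**The case against.** T3 is the first scheduled contact that falls after week 6 for every woman, so placing the full count there has a rationale. T2 does collect some visit data in person, and a T2 held close to week 6 could supply most or all of the count. Nothing in section 3.3 stops a woman from looking at her card during the call. These points stand. They make the size of the recall error uncertain, but they do not name a source of record or a way to combine T2 with T3.

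Several stronger readings are tempting, and the documents do not support them:

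- **Intention-to-treat makes bereaved women failures.** Section 4.0 fixes who is analysed and in which arm. It does not say how an unattainable outcome is coded.
- **A woman not reached by phone has no data.** She may have T2 data, and section 4.5 describes a contact list with phone numbers. Phone access is not an entry criterion in 3.2, however, and no fallback is described.
- **Intervention women are coached on these visits, so recall must differ by arm.** Section 3.5 does not list postnatal check-ups as session content. Differential recall is possible, and no masking of the research assistants is described, but it is an assumption.
- **Every neonatal death rules out success.** A newborn could have four check-ups and die later.
- **The death rule moves the result by 0.5–1.2 points.** That comes from 0.02 × 0.23 and 0.05 × 0.23. It applies the neonatal figure to stillbirths, for which section 1.2 gives 9%, and it leaves out multiplication by the attendance rate.
- **Overlap between Aims 2 and 3 is itself a defect.** The plan claims no independence, and Holm's procedure is valid under any dependence.

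There is also a fair objection to the remedy. Scoring bereaved women on maternal visits alone gives them an easier criterion, so a mortality difference could still move the outcome, in the other direction. That stands, and it is why the fix needs a supporting analysis that does not depend on infant survival.

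**Conclusion.** The concern holds as a gap in specification with a risk of misclassification; it is not a demonstrated bias. A primary outcome is listed as a count only by phone about 20 weeks after its window closes, and its scoring after a stillbirth or early infant death is not stated.

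The recall part matters more. Its size cannot be fixed from the documents. Under the assumed error rates it could shrink an OR of 1.50 to between 1.44 and 1.27, or create a false difference of 2.5–5 points if specificity differed by 5–10 points between arms. The death part is small, about 0.1–0.6 points at 50% attendance, under assumed losses of 2–5% and reductions of 9–23% borrowed from a different type of intervention. The case for a scoring rule therefore rests mainly on removing a choice that could be made after the data are seen.

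The change is worth making because the research assistant already interviews the woman and reads her card at T2.

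**What to change.** **Section 3.3.**
- At the in-person T2 visit, have the research assistant record the date of each maternal and each newborn check-up, from the card where it is written and otherwise by self-report.
- At T3, ask only about check-ups between the T2 date and day 42.
- Score the outcome on the merged dates, and do not count the research visit as a check-up. A woman with four dated check-ups for both by T2 is then scored whether or not T3 reaches her.

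**Section 2.0.** State that women with a stillbirth, or an infant death before the fourth check-up, are scored on the maternal component.

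**Section 4.0.**
- Report four maternal check-ups in all women as a supporting analysis, since it does not depend on infant survival.
- Add two sensitivity analyses: one that codes the women above as failures, and one that excludes them.

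**Cost.** A dated field on the T2 form, a narrower T3 question, outcome wording and three short extra analyses. T2 abstraction takes slightly longer. Only the two-day visit is now listed as card-recorded, so visits not written on the card would still rest on self-report, though with shorter recall than at six months.
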